1. PROTOCOL SYNOPSIS FOR STUDY 201749

Rationale

The primary purpose of this study is to demonstrate improvements in lung function in subjects treated with Umeclidinium/Vilanterol (UMEC/VI) compared with Umeclidinium (UMEC) for 24 weeks. A further important aspect of the study is to evaluate the effect of UMEC/VI, UMEC, and salmeterol with respect to health-related quality of life (HRQoL), measured through patient reported outcomes (PROs) questionnaires, and lung function. Additional assessments to further evaluate other measures of chronic obstructive pulmonary disease (COPD) efficacy and symptoms control will be performed.

Objective(s)/Endpoint(s)

Objectives	Endpoints
Primary	
 To compare the effect of UMEC/VI (62.5/25 mcg once daily) with UMEC (62.5 mcg once daily) on lung function Change from baseline in trough Forced Expiratory Volume in One Second (FEV₁) at week 24
Secondary	
 To compare UMEC/VI (62.5/25 mcg once daily), UMEC (62.5 mcg once daily) with salmeterol (50 mcg twice daily) on patient reported outcomes (PROs) Change from baseline in self administered computerised (SAC) transient dyspnea index (TDI) Percentage of TDI responders according to SAC TDI score. A responder is defined as a ≥ 1 unit improvement in SAC TDI score Assessment of respiratory daily symptoms over 24 weeks using Evaluating Respiratory Symptoms-COPD (E-RS) and its subscales (breathlessness, cough and sputum and chest symptoms) Percentage of E-RS responders according to E-RS score (defined as reduction in E-RS score of ≥ 2 or ≥ 3.35 units) from baseline Change from baseline in St George's Respiratory Questionnaire (SGRQ-C) Percentage of responders according to SGRQ-C total score (defined as a 4 point or greater reduction from

Objectives	Endpoints
	
baseline)
 
 • Change from baseline in COPD assessment test (CAT) • Percentage of responders according to CAT (defined as a ≥ 2 unit improvement in score from baseline)

Other
 
 • To compare UMEC/VI (62.5/25 mcg once daily), UMEC (62.5 mcg once daily) with salmeterol (50 mcg twice daily) on other COPD efficacy measures 	
 • Time to first mild, moderate or severe exacerbation • Time to moderate or severe exacerbation • Time to severe exacerbations • Time to clinically important deterioration (CID) composite endpoint • Time to clinically important deterioration composite endpoint excluding FEV₁ • Rescue albuterol/salbutamol use, (percentage of rescue-free days and mean number of Inhalations/day) captured by the electronic diary (eDiary) over 24 weeks • Inspiratory capacity (IC) • Full Vital capacity (FVC) • Change from baseline in trough FEV₁ • Change from baseline in global impression of disease severity

Objectives	Endpoints
Safety	

 To evaluate safety and tolerability of UMEC/VI (62.5/25 mcg once daily), UMEC (62.5 mcg once daily) and salmeterol 50 mcg twice daily) 	
 Incidence of adverse events
Exploratory	

 To explore the effect of UMEC/VI (62.5/25 mcg once daily), UMEC (62.5 mcg once daily) with salmeterol (50 mcg twice daily) on rate of COPD exacerbation 	
 Rate of mild, moderate or severe exacerbations Rate of moderate or severe exacerbation

 To compare albuterol/salbutamol use captured in the eDiary with the electronic metered dose inhaler (eMDI) device 	
 Rescue albuterol/salbutamol use, (percentage of rescue-free days and mean number of Inhalations/day) captured by the eMDI device over 24 weeks as data allow

 To explore the effect of UMEC/VI (62.5/25 mcg once daily), UMEC (62.5 mcg once daily) with salmeterol (50 mcg twice daily) on physical activity 	
 Change from baseline in physical activity

 To investigate the CID composite endpoint ability to predict short term outcomes 	
 To compare physical activity levels, ER-S, rescue medication use, exacerbations and mortality in subjects with and without a CID

Overall Design

This is a multi-centre, randomized, double blind, double dummy, 3-arm parallel group study. Eligible subjects will be randomized in a ratio of 1:1:1 to UMEC/VI inhalation powder (62.5/25 mcg once daily) administered via the ELLIPTA™ dry powder inhaler (DPI) or UMEC (62.5 mcg once daily) administered via the ELLIPTA DPI or salmeterol (50 mcg twice daily (BID)) administered via the DISKUS™ DPI.

There will be a total of 5 clinic visits and one follow-up phone call (Visit 6). A pre-screening visit (Visit 0) may be required in order to administer the informed consent before any changes are made to the subject's current medication regimen. If no changes in medication are required, V0 (pre-screening) and V1 (screening) may be conducted on the same day. Inhaled long-acting muscarinic antagonist (LAMA) or long-acting beta₂-agonist (LABA) and/or albuterol/salbutamol as needed (rescue medication) are not exclusionary prior to Screening or during the run-in.

Eligible subjects at Screening Visit 1 will be current or former smokers, at least 6 weeks ICS and ICS/LABA free with an FEV₁ post-albuterol/salbutamol of $\geq 30\%$ to $\leq 80\%$ predicted normal and a FEV₁/FVC < 0.7 and a CAT score ≥ 10 .

Subjects using inhaled LAMA or LABA medication must withhold their morning dose prior to Screening spirometry. Subjects who meet all other eligibility criteria at Screening will enter a run-in period for 4 weeks. During the run-in period, subjects will continue with their inhaled LAMA or LABA. In addition, subjects will be provided with short acting albuterol/salbutamol as needed for relief of COPD symptoms (rescue medication) throughout the study.

Subjects who experience a moderate or severe COPD exacerbation during the run-in period will be deemed run-in failures. Subjects who experience a mild COPD exacerbation, defined as worsening of symptoms that requires **no** treatment with antibiotics or steroids and is self managed by the patient by an increase of inhaled rescue medication will be able to continue in the study based on the judgment of the investigator and agreement of the sponsor's medical monitor.

At the randomization Visit 2 (Day 1), those subjects who successfully complete the run-in period, as well as meet the other pre-defined eligibility and randomization criteria, will be randomized to one of the 3 treatment arms for 24 weeks.

In addition, a subset of subjects (approximately 150 per treatment arm) will undergo assessment of their physical activity measured through a physical activity monitor (Actigraph GT9X) worn for 7 days from Screening (Visit 1), for 7 days from Randomisation (Visit 2), 7 days from Visit 3, and for 7 days prior to last clinic Visit (Visit 5).

The occurrence of adverse events (AEs) will be evaluated throughout the study beginning at Visit 2 (Day 1) and until the follow-up contact (Visit 6). Serious adverse events (SAEs) will be collected over the same time period as AEs. However, any SAEs assessed as related to study participation (e.g., study treatment, protocol-mandated procedures, invasive tests, or change in existing therapy) or related to a GSK concomitant medication, will be recorded from the time a subject consents to participate in the study up to and including any follow up contact.

All subjects will be given an electronic diary (eDiary) for use during the run-in, and the treatment period to complete PRO questionnaires, record COPD daily symptoms and the time they take their COPD medications. Daily rescue medication usage (number of inhalations taken in the last 24 h) will also be captured in the eDiary. In addition, and in some countries, rescue medication use will also be captured by the use of electronic metered dose inhaler (eMDI).

At Screening Visit 1, all subjects must be trained on the proper use of their existing COPD medications inhalation devices and instructed to strictly adhere to and record the time they take their COPD medications in the eDiary.

At the randomization Visit 2, all subjects must be trained on the proper use of the ELLIPTA and DISKUS inhalation devices and instructed to strictly adhere to and record the time they take their study medications in the eDiary.

All subjects must be trained on the correct use of the eDiary and instructed to complete the eDiary during the run-in and treatment period.

Subjects will be considered to have completed the study upon completion of the Follow-Up contact by telephone.

[figure not shown]
There are no plans to routinely provide any of the study treatments for compassionate use following study completion as the study treatment are commercially available.

Treatment Arms and Duration

Subjects will be stratified based on long-acting bronchodilator usage during the run-in (none or one long-acting bronchodilator per day) and randomized in a ratio of 1:1:1 to either

- UMEC/VI 62.5/25 mcg once daily via ELLIPTA + placebo twice daily via DISKUS
- UMEC 62.5 mcg once daily via ELLIPTA + placebo twice daily via DISKUS
- Salmeterol 50 mcg twice daily via DISKUS + placebo once daily via ELLIPTA

Study schematic

*Subjects may continue the use of inhaled LAMAs or LABAs and/or study provided albuterol/salbutamol as needed (rescue medication) during the run-in while adhering to the withholding of other COPD medications detailed in the Exclusion Criteria.

Type and Number of Subjects

Approximately 3232 subjects will be screened, such that 2424 subjects will be randomized and approximately 2181 evaluable subjects complete the study.

Analysis

The primary purpose of this study is to demonstrate improvements in lung function for subjects treated with UMEC/VI compared with UMEC for 24 weeks.

The primary endpoint is change from baseline in trough FEV₁ at Week 24.

The null hypothesis is no difference between treatment groups ($H_0: \mu_T - \mu_S = 0$), with the alternative hypothesis that there is a difference between treatment groups ($H_1: \mu_T - \mu_S \neq 0$), where μ_T is the mean change from baseline for UMEC/VI and μ_S is the mean change from baseline for UMEC.

The primary endpoint of mean change from baseline in trough FEV₁ at the end of Week 24 will be analysed using Mixed Models repeated Measures (MMRM) analysis. The MMRM analysis will include measurements at Treatment Weeks 4, 12 and 24. Treatment group (a categorical variable) will be fitted as the explanatory variable with appropriate pre-defined variables, stratum (number of bronchodilators per day during run-in) and baseline values, fitted as covariates. Visit (nominal) will be fitted as a categorical variable and visit-by-baseline and visit-by-treatment interaction terms will be included to allow treatment effects to be estimated at each visit separately. The variance covariance matrix

will be assumed to be unstructured (based on previous experience no issues are expected with fitting models with this matrix structure).

The estimated treatment differences between UMEC/VI versus UMEC for each endpoint will be presented with the 95% confidence intervals for the difference and the p-value.

2. INTRODUCTION

2.1. Study Rationale

Chronic obstructive pulmonary disease (COPD) is associated with poor health-related quality of life (HRQoL). Pharmacologic therapy is used to improve lung function, reduce symptoms, frequency and severity of exacerbations, and improve patients HRQoL [GOLD, 2015]. Umeclidinium/Vilanterol (UMEV/VI 62.5/25 mcg) is indicated for the maintenance treatment of COPD that contain long-acting muscarinic antagonist (LAMA) and long-acting beta₂-agonist (LABA) bronchodilators. Umeclidinium (UMEV) is indicated as a maintenance bronchodilator treatment to relieve symptoms in adult patients with COPD. Salmeterol has long been used for symptoms management of COPD. However, a direct comparison of these maintenance therapies has not been conducted with respect to HRQoL.

The primary purpose of this study is to demonstrate improvements in lung function for subjects treated with UMEC/VI compared with UMEC for 24 weeks. The effect of UMEC/VI, UMEC, and salmeterol with respect to patient HRQoL measured through patient reported outcomes (PROs) questionnaires, symptoms and lung function will also be evaluated.

2.2. Brief Background

COPD is characterized by an airflow limitation which is not fully reversible, usually progressive and accompanied by a chronic cough, sputum production and dyspnea which can be a major cause of disability and anxiety associated with the disease [Maleki-Yazdi, 2014]

Furthermore, acute exacerbations contribute to the overall severity of disease as these episodes are accompanied by worsened symptoms and are associated with increased decline in lung function and mortality [Wedzicha, 2013; Schmidt, 2014].

Pharmacologic therapy is used to improve lung function, reduce symptoms, reduce the frequency and severity of exacerbations, and also to improve health status and exercise tolerance. Maintenance treatment is recommended primarily through the use of LABAs or LAMAs. COPD treatment guidelines recommend an incremental approach to pharmacological treatment as the disease state worsens, involving the use of combinations of drug classes with different or complementary mechanisms [GOLD, 2015].

UMEV/VI inhalation powder is a combination of UMEC (umeclidinium bromide), a LAMA, and VI (Vilanterol), a LABA, delivered via the ELLIPTA dry powder inhaler

(DPI). UMEC/VI at a dose of 62.5/25mcg once-daily is marketed in the United States (US) and Europe under the trade name ANORO™ ELLIPTA.

UMEC (62.5 mcg) inhalation powder is marketed in the United States (US) and Europe under the trade name INCRUSE™ ELLIPTA. UMEC (62.5mcg) is indicated as a maintenance bronchodilator treatment to relieve symptoms in adult patients with COPD. UMEC (62.5 mcg) improves forced expiratory volume in one second (FEV₁), dyspnea and HRQoL whether used as monotherapy [Trivedi, 2014; Feldman, 2016] or as an add on to fluticasone propionate and vilanterol (FF/VI) [Siler, 2015]. Salmetrol (50 mcg) DISKUS is a long-acting broncholdilator that has long been used for the maintenance treatment of COPD [Tashkin, 2010].

Clinically important deterioration (CID) is a novel, exploratory composite endpoint which assesses individual deteriorations in lung function and in patient PROs defined by the accepted minimal clinically important difference (MCID), as well as the incidence of moderate to severe exacerbations [Singh, 2016], (Section 7.3.5). CID will be analysed to determine whether UMEC/VI (62.5/25mcg) therapy provides greater clinical stability as compared with UMEC and salmeterol monotherapies.

3. OBJECTIVE(S) AND ENDPOINT(S)

Objectives	Endpoints
Primary	

 To compare the effect of UMEC/VI (62.5/25 mcg once daily) with UMEC (62.5 mcg once daily) on lung function 	
 Change from baseline in trough Forced Expiratory Volume in One Second (FEV₁) at week 24
Secondary	

 To compare UMEC/VI (62.5/25 mcg once daily), UMEC (62.5 mcg once daily) with salmeterol (50 mcg twice daily) on patient reported outcomes (PROs) 	
 Change from baseline in self administered computerised (SAC) transient dyspnea index (TDI) Percentage of TDI responders according to SAC TDI score. A responder is defined as a ≥ 1 unit improvement in SAC TDI score Assessment of respiratory daily symptoms over 24 weeks using Evaluating Respiratory Symptoms-COPD (E-RS) and its subscales (breathlessness, cough and sputum and chest symptoms) Percentage of E-RS responders according to E-RS score (defined as reduction in E-RS score of ≥ 2 or ≥ 3.35 units) from baseline

Objectives	Endpoints
	
 Change from baseline in St George's Respiratory Questionnaire (SGRQ-C) Percentage of responders according to SGRQ-C total score (defined as a 4 point or greater reduction from baseline) Change from baseline in COPD assessment test (CAT) Percentage of responders according to CAT (defined as a ≥ 2 unit improvement in score from baseline)
Other 
 To compare UMEC/VI (62.5/25 mcg once daily), UMEC (62.5 mcg once daily) with salmeterol (50 mcg twice daily) on other COPD efficacy measures 	
 Time to first mild, moderate or severe exacerbation Time to moderate or severe exacerbation Time to severe exacerbations Time to clinically important deterioration (CID) composite endpoint Time to clinically important deterioration composite endpoint excluding FEV₁ Rescue albuterol/salbutamol use, (percentage of rescue-free days and mean number of Inhalations/day) captured by the electronic diary (eDiary) over 24 weeks Inspiratory capacity (IC) Full Vital capacity (FVC) Change from baseline in trough FEV₁ Change from baseline in global impression of disease severity

Objectives	Endpoints
Safety	

 To evaluate safety and tolerability of UMEC/VI (62.5/25 mcg once daily), UMEC (62.5 mcg once daily) and salmeterol 50 mcg twice daily) 	
 Incidence of adverse events
Exploratory	

 To explore the effect of UMEC/VI (62.5/25 mcg once daily), UMEC (62.5 mcg once daily) with salmeterol (50 mcg twice daily) on rate of COPD exacerbation 	
 Rate of mild, moderate or severe exacerbations Rate of moderate or severe exacerbation

 To compare albuterol/salbutamol use captured in the eDiary with the electronic metered dose inhaler (eMDI) device 	
 Rescue albuterol/salbutamol use, (percentage of rescue-free days and mean number of Inhalations/day) captured by the eMDI device over 24 weeks as data allow

 To explore the effect of UMEC/VI (62.5/25 mcg once daily), UMEC (62.5 mcg once daily) with salmeterol (50 mcg twice daily) on physical activity 	
 Change from baseline in physical activity

 To investigate the CID composite endpoint ability to predict short term outcomes 	
 To compare physical activity levels, ER-S, rescue medication use, exacerbations and mortality in subjects with and without a CID

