7.3.4. COPD Exacerbation

A mild exacerbation is defined as worsening of symptoms that require no treatment with antibiotics or steroids, and is self managed by the patient by an increase of inhaled rescue medications. A moderate COPD exacerbation is defined as worsening symptoms of COPD that require treatment with oral/systemic corticosteroids and/or antibiotics. A severe exacerbation is defined as worsening symptoms of COPD that require in-patient hospitalization or emergency room for longer than 24 hrs.

If a subject experiences a mild, moderate or severe COPD exacerbation, the COPD exacerbation page of the eCRF should be completed. COPD exacerbations should not be recorded as an AE, unless they meet the definition of a SAE. Details of COPD exacerbation identification, categorization and treatment guidelines are described in [Appendix 5](#).

Subjects who experience a mild exacerbation during the run-in period will not be withdrawn from the study. However, subjects who experience moderate or severe exacerbation during the run-in period will be withdrawn from the study and will not be allowed to be re-screened.

Subjects, who experience a mild, moderate or severe exacerbation during the treatment period, will **not** be withdrawn from the study unless the investigator or GSK medical monitor thinks it is best for the patient to withdraw from the study.

Signs and symptoms of COPD included on the electronic diary cards will not be considered AEs and will not be recorded in the eCRF.

The time period for collection of COPD exacerbations will be from the Pre-Screening (Visit 0) until completion of the follow-up contact. If a subject experiences a COPD exacerbation from the time the ICF is signed until randomization, summary information (yes/no status question) will be collected in the eCRF. COPD exacerbations after randomization through follow-up will be recorded on the COPD exacerbation page of the eCRF.

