7.3.5. Clinically important deterioration (CID)

Clinically important deterioration (CID) is a composite endpoint defined as:

- A decrease of ≥ 100 mL from baseline in trough FEV₁
- A deterioration in HRQoL defined as ≥ 4 units increase from baseline in SGRQ
- The occurrence of an on-treatment moderate/severe COPD exacerbation

In addition, this study will explore CAT and TDI PROs as part of the composite endpoint.

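### The exploratory test of whether CID predicts outcomes names exacerbations as an outcome, although an on-treatment moderate/severe exacerbation is itself part of CID and no time order is set

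*Protocol*

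**What the plan says.** The last exploratory objective in Protocol Section 3 (repeated in the synopsis) is "To investigate the CID composite endpoint ability to predict short term outcomes". Its endpoint is "To compare physical activity levels, ER-S, rescue medication use, exacerbations and mortality in subjects with and without a CID".

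Section 7.3.5 defines CID by three components:

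- a fall of at least 100 "mL from baseline in trough FEV₁";
- "A deterioration in HRQoL defined as" a rise of at least 4 units in SGRQ;
- "The occurrence of an on-treatment moderate/severe COPD exacerbation".

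Section 2.2 describes the composite in the same way: lung function and PRO deteriorations "as well as the incidence of moderate to severe exacerbations". The variant listed among the other endpoints is "Time to clinically important deterioration composite endpoint excluding FEV₁". Section 7.3.5 also proposes to explore CAT and TDI within the composite. Every version described therefore keeps the exacerbation component.

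Exacerbations of all severities are recorded (Section 7.3.4: "If a subject experiences a mild, moderate or severe COPD exacerbation, the COPD exacerbation page of the eCRF should be completed"), up to the follow-up contact. The protocol does not say when CID status is fixed for this comparison or over what period the outcomes are counted.

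**The concern.** The objective is about prediction, so the predictor should be settled before the outcome is observed. Here one kind of event can do both jobs: a moderate/severe exacerbation on treatment puts a subject in the CID group and is then counted as an outcome of that group. On a plain reading, CID yes or no over the study, that part of the contrast is fixed by the definition.

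The other outcomes have a different and weaker problem. They are not part of CID, but they may have been measured before the CID occurred. Section 2.2 calls CID novel and exploratory, and this is the only objective in the protocol that examines its predictive value. An association that is built in, or that runs backwards in time, could be mistaken for evidence that the composite predicts.

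**Working it through.** The protocol gives no figure for this comparison, so there is nothing to reproduce. The check sets the definitions side by side and then sizes the built-in difference in a null case.

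**Step 1: logic.** Let E be an on-treatment moderate/severe exacerbation and D the FEV₁ or SGRQ component. Section 7.3.5 gives CID = D or E. Over one common treatment period, no CID implies no E, so P(E | no CID) = 0 whatever the true rates are.

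**Step 2: size under no association.** Take E and D as independent, so that the other components carry no information about exacerbations. With p_E = P(E) and p_D = P(D):

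- P(CID) = 1 − (1 − p_E)(1 − p_D)
- P(E | CID) = p_E / P(CID)

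Neither rate is in the protocol, so both are assumed.

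| p_E | p_D | P(CID) | P(E given CID) | P(E given no CID) |
|---|---|---|---|---|
| 15% | 40% | 1 − 0.85 × 0.60 = 0.49 | 0.15/0.49 = 30.6% | 0% |
| 10% | 50% | 1 − 0.90 × 0.50 = 0.55 | 0.10/0.55 = 18% | 0% |
| 20% | 30% | 1 − 0.80 × 0.70 = 0.44 | 0.20/0.44 = 45% | 0% |

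The last two rows are the extremes for p_E from 10% to 20% and p_D from 30% to 50%. The zero does not depend on these inputs; only the size of the other figure does.

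**Step 3: outcomes that are not components.** Mild exacerbations, activity, E-RS, rescue use and mortality do not define CID, so no difference is forced. Their difficulty is timing. After baseline, spirometry and SGRQ-C are scheduled only at Weeks 4, 12 and 24 (Section 7.1). A CID first found through FEV₁ or SGRQ at Visit 5 comes after essentially all the 24-week diary data, and after all four activity periods (7 days from Visits 1, 2 and 3, and the 7 days before Visit 5). That CID cannot predict those data.

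**Step 4: does the remedy remove the artefact?** In the same null case with p_E = 15%:

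- Dropping the exacerbation component leaves CID = D. By independence, P(E | D) = P(E | not D) = 15%.
- With a Week 12 landmark and a constant exacerbation rate (a further assumption), the risk over the remaining 12 weeks is 1 − 0.85^(12/24) = 1 − 0.922 = 7.8% in both groups, ignoring withdrawals.

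Either change removes the built-in difference.

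**The case against.** The strongest reply is that the protocol never says CID status and exacerbations share one window. Prediction implies that CID comes first, and Section 9.4.2 leaves detail on other efficacy endpoints to the RAP, which is not shown. A landmark or a reduced composite could be set there. This stands in part: the 0% arises only for a common window, and the protocol does not commit to one. But the protocol itself fixes the groups and the outcomes, names a component of the predictor among the outcomes, and gives no time order. A possible later repair does not make that wording sound.

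A reader might infer more than the documents support:

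- **That any exacerbation is a CID.** Only on-treatment moderate/severe events are. Mild events are recorded but are not a component. A moderate/severe event after treatment ends but before the follow-up contact can occur in a subject without a CID.
- **That the whole comparison is circular and shows nothing.** Activity, E-RS, rescue use and mortality are outside the definition, and their contrasts could turn out null.
- **That early leavers necessarily distort the result because they miss CID visits.** The FEV₁ and SGRQ components do need a visit, but the exacerbation component does not, and the protocol gives nothing from which to size the effect.

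The case against also notes, correctly, that the objective is exploratory and that no treatment comparison depends on it.

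**Conclusion.** The point holds for one outcome in full and for the rest in a weaker form. If CID status and exacerbations are both taken over the treatment period, the contrast in on-treatment moderate/severe exacerbations says nothing about prediction. In the null case it is 30.6% v 0% at the central assumptions, and 18% to 45% v 0% over the range shown. These figures rest on assumed rates and on independence; the zero rests on the definition alone. For mild exacerbations, activity, E-RS, rescue use and mortality, the lack of a time order means the comparison shows association and not prediction. The text does not support calling those outcomes circular. The consequence is confined to an exploratory objective, and primary and secondary conclusions are unaffected.

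**What to change.** State a landmark for this objective. Among subjects still in the study at Visit 4 (Week 12), classify CID status up to Visit 4 and compare only what follows, adjusted for treatment and baseline:

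- exacerbations with onset after Visit 4 (onset dates are recorded, Section 12.5.6);
- E-RS and rescue use in Weeks 13 to 24, from the daily diary;
- activity in the 7 days before Visit 5;
- deaths after Visit 4.

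For the exacerbation outcome, add a sensitivity analysis with a CID version that omits the exacerbation component. It shows whether the FEV₁ and SGRQ parts carry information beyond a previous exacerbation.

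The change costs analysis wording only and needs no new data. Its downsides should be stated:

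- Outcomes cover 12 weeks rather than 24.
- Subjects withdrawn before Visit 4 leave the landmark set and should be reported. They include those withdrawn under the Section 5.5.1 stopping criterion of two moderate or one severe exacerbation.
- That criterion also shortens later follow-up more often in subjects whose CID was an exacerbation, so later exacerbations should be analysed with allowance for time at risk.

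How much follow-up is lost depends on how withdrawal is applied. Section 5.5.1 requires withdrawal at that threshold, whereas Section 7.3.4 says subjects with an on-treatment exacerbation stay in unless the investigator or medical monitor judges otherwise. The two sections must be reconciled.
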